#### 4.4.8. Treatment Compliance

All subjects are to receive 4 doses of study product (see Table 1) administered in the clinic.

## 4.5. Immunogenicity and Safety Variables

For additional details on study procedures and evaluations by study visits/days, see [Table 2](#).

Safety will be assessed by the frequency and/or severity of:

- Solicited injection site and systemic reactogenicity events from the time of each vaccination through Day 7 after each vaccination, overall and in each vaccination group.
- Serious adverse events (SAEs) considered study vaccine-related and reported at any time after the first vaccination through the end of this trial, overall and in each vaccination group.
- Vaccine-related lab AEs through study Day 22, overall and in each vaccination group.
- Unsolicited vaccine-related AEs from the time of the first vaccination through Day 28 after the last vaccination, overall and in each vaccination group.
- New onset chronic medical conditions at any time after the first vaccination and through the end of this trial, overall and in each vaccination group.
- Local, systemic or lab toxicities after any vaccination, overall and in each vaccination group.
- Local reactogenicity through Day 7 after any vaccination, overall and in each vaccination group.
- Any SAEs, overall and in each vaccination group.

Immunogenicity will be assessed by:

- Proportion of subjects seroconverting to rabies virus at each antibody time point (seroconversion is defined as VNA concentration  $\geq 0.5$  IU/mL), in each vaccination group and overall.
- GMT (as measured by rabies VNA using a standard, WHO-approved, RFFIT) at each antibody time point within each vaccination group.
- Peak GMT (as measured by rabies VNA using a standard, WHO-approved, RFFIT; peak GMT is defined as the geometric mean of the highest titer per subject across all post-vaccination antibody time points) within each vaccination group.
- Frequencies of circulating T cell responses against RG by ex vivo IFN-ELISpot.
- Characteristics of circulating CD4 and CD8 T cell responses against RG by multiparameter ICS.
- Magnitude and durability of RG-specific memory B cells by ELISpot.
- GMT to ChAd155 vector at one month after first vaccination.

## 5. SAMPLE SIZE CONSIDERATIONS

This trial will enroll 50 subjects into four vaccination groups: Group A (N=14) will receive one dose of ChAd155-RG at the lower dosage ( $5 \times 10^{10}$ vp); Group B (N=14) will receive one dose of ChAd155-RG at the higher dosage ( $1 \times 10^{11}$ vp); Group C (N=10) will receive two doses of ChAd155-RG at the higher dosage ( $1 \times 10^{11}$ vp); and Group D (N=12) will receive three doses of RABAVERT.

The sample size of 10-14 subjects in each vaccination group is small given the early stage (Phase I) of the product's development; thus, the precision of estimates for AEs is limited. Rare AEs associated with dose level or number of doses are not demonstrable in a trial of this size; however, the probabilities of observing one or more AEs within a vaccination group given various true event rates are presented in [Table 3](#). The minimum detectable event rates for various levels of power are displayed in [Table 4](#).

This trial was not designed to formally test any hypotheses associated with the immunogenicity data. The 95% confidence intervals (CIs) for various observed seroconversion rates at various sample sizes were calculated assuming observed seroconversion rates of 90%, 95%, and 100%, as shown in [Table 5](#).

## 6. GENERAL STATISTICAL CONSIDERATIONS

### 6.1. General Principles

All continuous variables will be summarized using the following descriptive statistics: n (non-missing sample size), mean, standard deviation (SD), median, maximum, and minimum. The frequency and percentages (based on the non-missing sample size) of observed levels will be reported for all categorical measures. In general, all data will be listed, sorted by vaccination group and subject, and when appropriate by visit number within subject. All summary tables will be structured with a column for each vaccination group in the following order: low dose, high dose (x1), high dose (x2), RABAVERT and All Subjects, and will be annotated with the total population size relevant to that table, including any missing observations.

### 6.2. Timing of Analyses

One interim analysis is planned for this study. It will be performed after at least half the subjects complete Day 91 and after VNA data through Day 91 are received for subjects for whom data are available at the time of database freeze.

The primary CSR will summarize all safety and all primary and secondary protocol-specified humoral immunogenicity endpoint results collected through Day 381.

### 6.3. Analysis Populations

#### 6.3.1. Modified Intention-to-Treat (mITT) Population

The modified intent-to-treat (mITT) population includes all subjects who received at least one dose of study vaccine and contributed both pre- and at least one post-study vaccination venous blood samples for immunogenicity testing for which valid results were reported. For analyses using the mITT population, subjects will be grouped based on randomized treatment arm.

#### 6.3.2. Per Protocol Population

The per protocol (PP) population includes all subjects in the mITT subset with the following exclusions:

- Data from all available visits for subjects found to be ineligible at baseline, according to the inclusion and exclusion criteria at the time of the subject's enrollment.
- Data from subjects who have a baseline rabies VNA concentration  $\geq 0.5$  IU/mL (for the immunogenicity analyses).
- Data from all visits subsequent to the following, such as:
  - Study withdrawal or treatment discontinuation
  - Any study vaccination dose received out of window
  - Receipt of non-study licensed live vaccine within 30 days before or after each study vaccination
  - Receipt of non-study licensed inactivated vaccine within 14 days before or after each study vaccination
  - Receipt of immunosuppressive therapy (e.g., corticosteroids) within 30 days before or after each study vaccination

- Receipt of chloroquine or hydroxychloroquine
- Data from any visit that occurs out of window, as defined in [Table 2](#) “Window for each study visit”.

### 6.3.3. Safety Population

The Safety Population will consist of all subjects who have received at least one dose of vaccine and for whom any data on safety are available. Subjects will be classified according to the vaccine and dosage received. The primary safety analysis will be performed using this population.

## 6.4. Covariates and Subgroups

The protocol does not define any formal subgroup analyses, and the study is not adequately powered to perform subgroup analyses.

## 6.5. Missing Data

Missing safety and/or immunogenicity data will not be imputed. No search for outliers will be performed. However, the logarithmic transform will be used as appropriate to improve the distributional properties of the data and reduce the impact of potential outliers.

## 6.6. Interim Analyses and Data Monitoring

For purposes of planning subsequent research and to allow internal and external presentations of data (e.g., national and/or international conferences and early publication of data), there will be one planned interim safety and immunogenicity analysis of subjects in the safety and modified intent to treat populations, respectively. Results of the interim analysis will not be used to make any decisions concerning the conduct of this trial.

Once at least half the subjects complete the Day 91 visit the clinical database will be cleaned, monitored and frozen by the SDCC. Group-unblinded analyses of safety, reactogenicity and available immunogenicity data are planned. The interim report will be prepared by the SDCC after the interim clinical database is frozen and all VNA data through Day 91 for subjects for whom data are available at the time of database freeze are received.

For this interim report, investigators will remain blinded to individual subject treatment assignments and will only be provided with data summaries aggregated by dose-group. Any data listings at the subject level will be blinded to vaccination group.

For the purpose of advancing from each group of sentinel subjects to the enrollment of all remaining subjects, the SMC will review all available safety data. Furthermore, the halting rules described in Section 9.5 of the study protocol will be utilized to pause this trial if certain criteria are met.

### 6.6.1. Interim Safety Review

Safety data for the first set of four sentinel subjects will not be reviewed by the SMC before enrollment of the second set of four sentinel subjects if no pre-defined halting rule is met. Safety data for all 8 sentinels will be reviewed by the SMC prior to enrollment of the remaining 42 subjects. These sentinel reviews will not involve hypothesis testing and will not be considered in estimating the precision of any estimates made at the conclusion of this trial.

The interim analysis will include all safety and immunogenicity data through Day 91 for subjects in the safety population for whom data are available at the time of database freeze. The interim safety analyses will include tables summarizing demographics, study status and protocol adherence information. Tables and figures will present unsolicited adverse events by MedDRA System Organ Class (SOC) and Preferred Term (PT), severity and relationship to study product. Solicited adverse events will be summarized by symptom, severity, and study day. Laboratory results will be summarized by parameter, severity, and study day. Blinded listings of early terminations, protocol deviations and clinical data may be included. Since this early analysis of the data is not intended to impact the conduct of this trial, it will have no impact on Type I error and adjustments are not planned.

#### **6.6.2. Interim Immunogenicity Review**

The interim analysis will include all available immunogenicity (VNA-RFFIT) data through Day 91 for the subjects in the mITT population for whom data are available at the time of database freeze, addressing secondary objectives. The interim immunogenicity analysis will include summaries of geometric mean titers (GMTs) and their associated 95% confidence intervals as well as peak GMT by vaccination group at study timepoints outlined in [Table 2](#). Titer results will also be displayed in reverse cumulative distribution (RCD) curves by visit and vaccination group. No hypothesis tests or modeling will be included in the interim immunogenicity analysis. Since this early analysis of the data is not intended to impact the conduct of this trial, it has no impact on Type I error and adjustments are not planned.

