**Figure 7: Rabies VNA Geometric Mean Titer and 95% CI Over Time Point by Vaccination Group - Per Protocol Population**

**Figure 8: Proportion of Subjects Seroconverting to Rabies Virus by Time Point and Vaccination Group - Modified Intent to Treat Population\***

[Implementation Note: For preliminary analyses, data collected through the data cut-off date will be displayed. Seroconversion is a post-vaccination serum antibody level  $> 0.5$  IU/mL.]

Asterisks = Proportion (%) of seroconverters.

Bars represent the exact, Clopper-Pearson, 95% CIs.

Any Time indicates proportion who seroconverted at any time.

[figure not shown]
Figure with similar format:

**Figure 9: Proportion of Subjects Seroconverting to Rabies Virus by Time Point and Vaccination Group – Per Protocol Population**

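### Interim peak titre and any-time seroconversion include subjects who have not yet reached Day 29, which biases these rows low, slightly more in Group C and the RABAVERT arm

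*SAP*

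**What the plan says.** The single interim is triggered by partial follow-up. SAP 6.2 states: "It will be performed after at least half the subjects complete Day 91". SAP 6.6 repeats it: "Once at least half the subjects complete the Day 91 visit the clinical database will be cleaned, monitored and frozen by the SDCC". No minimum follow-up is set for the other subjects.

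For neutralising antibody, SAP 6.6.2 reads: "The interim analysis will include all available immunogenicity (VNA-RFFIT) data through Day 91 for the subjects in the mITT population". Under SAP 6.3.1 the mITT population needs one dose and subjects who "contributed both pre- and at least one post-study vaccination venous blood samples for immunogenicity testing". A valid Day 1 and Day 8 result is therefore enough.

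The asterisked (interim) outputs include:
- Table 21, which has a post-vaccination peak row below the visit rows. Its footnote drops Days 181 and 381 at the interim but gives no rule for the peak row.
- Figures 4 and 6, which add each subject's maximum post-baseline titre.
- Figure 8, whose shell notes: "Any Time indicates proportion who seroconverted at any time".

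Peak GMT is defined in two ways. SAP 3.2.2 (and Protocol 3.2.2) makes it the highest of the visit GMTs. SAP 4.5 makes it the geometric mean of each subject's highest titre; SAP 3.3 and the Figure 6 shell also work per subject.

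SAP 6.6 gives the purpose as planning further research and "to allow internal and external presentations of data".

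**The concern.** A running maximum and an ever/never status are cumulative. For a subject sampled only at Day 8, the peak is the Day 8 titre. If that is below the quantification limit it enters as 0.05 IU/mL (SAP 8.2.1). At that point Group C has not had its second active dose (Day 15), nor RABAVERT its third (Day 22), and a single-dose subject may not have responded yet. More follow-up can raise these values but never lower them, so the direction of the bias is known.

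At stake is the accuracy of figures meant for conferences, early publication and design of the next study. The SAP's remark that the interim has no effect on Type I error does not bear on a biased estimate.

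**Working it through.** The documents give no figure for this bias. The counts that feed it agree: 14 + 14 + 10 + 12 = 50 subjects, 50 − 8 sentinels = 42, and half of 50 = 25.

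**Inputs from the documents.** Sentinels: 3 in A, 3 in B, 2 in D, none in C (SAP Table 1), so the 42 others split 11:11:10:10. Enrolment: up to 18 months (Protocol Summary), later slower than expected (SAP 15.1). Samples: Days 8, 15, 22, 29 and 91.

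**Assumptions.** Uniform accrual over T = 18 months (548 days), with 36 months (1,096 days) as the slow case; sentinels first; freeze when the 25th subject reaches Day 91.

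**Step 1, who is incomplete.** Let r = 50/T per day: 0.0913 at 18 months, 0.0456 at 36.
- Dosed at the freeze: 25 + 90r = 33.2 (29.1 at 36 months).
- Short of Day 29: 28r = 2.6 (1.3).
- Of these, not yet at Day 8, so not yet in mITT: 7r = 0.6 (0.3).
- In mITT but short of Day 29: 21r = 1.9 of 32.6 (1.0 of 28.8).

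For an arm with s sentinels and w non-sentinels, the number in mITT is s + (17 + 83r)w/42, and the number short of Day 29 is 21r·w/42.

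**Step 2, effect on peak GMT.** If a share f of an arm sits on average d log10 below its eventual peak, the ratio to the complete value is 10^(−f·d). The documents give no human titre by day, so d is assumed. I took 2.0 log10 at Day 8 (0.05 against 5 IU/mL). At Days 15 and 22 I took 0.3 and 0.1 in A/B, 0.7 and 0.3 in C, 1.0 and 0.3 in D. The three one-week bands are equally filled, so mean d is 0.8, 1.0 and 1.1.

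| Arm | f, 18 months | f, 36 months | d | Ratio, 18 months | Ratio, 36 months |
|---|---|---|---|---|---|
| A, B (each) | 0.50/9.44 = 5.3% | 0.25/8.44 = 3.0% | 0.8 | 0.91 | 0.95 |
| C | 0.46/5.85 = 7.8% | 0.23/4.95 = 4.6% | 1.0 | 0.84 | 0.90 |
| D | 0.46/7.85 = 5.8% | 0.23/6.95 = 3.3% | 1.1 | 0.86 | 0.92 |

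Simulating whole trials gives about the same: at 18 months A/B 0.90 to 0.91, C 0.83 and D 0.86; at 36 months C 0.90 and D 0.92. A milder shortfall of 0.3 log10 would put Group C at 10^(−0.078 × 0.3) = 0.95 at 18 months.

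**Step 3, any-time seroconversion.** If all subjects would eventually seroconvert and none had done so before Day 29, the loss equals f: 5.3 points in A/B, 7.8 in C and 5.8 in D at 18 months. That is an upper bound. If only those with nothing beyond Day 8 are below 0.5 IU/mL, the loss in C is 0.15/5.85 = 2.6 points.

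**Step 4, chance in a small arm.** Group C has about 6 subjects at the freeze. One with only a Day 8 value of 0.05, against 5 in the others, divides peak GMT by (5/0.05)^(1/6) = 2.15. If the other five have seroconverted, any-time reads 5/6 = 83% (exact 95% CI 36% to 99.6%) instead of 5/5 = 100% (48% to 100%).

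**Step 5, which cut-off.** In simulation (SD 0.4 between and 0.2 within subjects, log10), the root mean square error of Group C's log10 peak at 18 months is 0.25 on all data, 0.24 in Day 91 completers and 0.20 in subjects past Day 29. Requiring Day 91 removes 90r = 8.2 subjects, and Group C falls from about 6 to 4.

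**The case against.** The best defence has four parts. No trial decision depends on the interim, and the final report has full follow-up. The secondary endpoint defines peak GMT as the highest visit GMT; under that definition incomplete subjects simply drop out of later visits and cause no systematic downward bias. Incomplete follow-up is already visible, since interim Table 14 counts by arm those fully vaccinated and those who completed Day 91. And slow accrual, which the SAP reports, shrinks the incomplete share.

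The first and last points stand and keep this modest. The second shows a conflict of definitions but does not remove the problem: SAP 4.5 and the Figure 4 and 6 shells use per-subject maxima, and Figure 8 is ever/never under either definition. The third helps only partly: Table 14 shows that follow-up is incomplete, but the peak row still counts everyone with any post-dose sample.

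A reader might also infer that interim adverse event rates are seriously understated, especially for RABAVERT. SAP 6.6.1 does say "The interim analysis will include all safety and immunogenicity data through Day 91 for subjects in the safety population for whom data are available", and the safety population is "all subjects who have received at least one dose of vaccine and for whom any data on safety are available", so cumulative Tables 29, 70 and 75 do include subjects inside the 28-day window (Day 22 + 28 = Day 50). But SAP 9.3 includes every reported event, so only events still to come are missing. At 18 months, 12.2% of dosed subjects in A/B, 17.7% in C and 13.3% in D are short of Day 50; under an assumed flat hazard the relative shortfall is half that, about 6%, 9% and 7%. RABAVERT does not stand out. The per-dose solicited Tables 31 to 35 carry no asterisk, and the starred day-by-day Tables 36 to 65 already use subjects with data at each time point.

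**Conclusion.** The point holds for the cumulative immunogenicity rows. Followed as written, the SAP gives interim peak GMT and any-time seroconversion that are biased low whenever subjects are still before Day 29 at the freeze. Under the stated assumptions peak GMT is about 0.90 to 0.95 of its complete value in A and B and 0.83 to 0.92 in C and D. The larger effect in C comes from having no sentinels and a second active dose on Day 15; in D it comes from a third active dose on Day 22.

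The size rests on assumed accrual and kinetics; no human day of peak titre is given for any arm. Faster accrual would enlarge it, and it disappears if everyone has passed Day 29. The peak GMT part applies only to the per-subject definition.

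Two stronger readings are not supported. The planned between-arm contrasts are not distorted: Table 23 compares seroconversion visit by visit, and no interim contrast of peak or any-time response is planned. Nor is a twofold drop in Group C's peak GMT the expected result: at 18 months about 7r = 0.64 Day-8-only subjects are expected across all arms, 0.15 of them in Group C.

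**What to change.** 1. In SAP 6.6.2 and the shells for Table 21 and Figures 4, 6 and 8, state that interim peak and any-time results use only mITT subjects who have reached the Day 29 sample. Keep by-visit results on all available data.
2. Reconcile the peak GMT definitions in SAP 3.2.2 (and Protocol 3.2.2) with SAP 3.3 and 4.5, so that the Table 21 row has one meaning.
3. Leave Tables 29, 70 and 75 on all dosed subjects with all reported events. At most, add the number past Day 50 by arm. Restricting them would remove reported events, including serious ones, from a safety summary.

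The cost is a sentence, a subset flag and a footnote. At 18 months about two to three of roughly 33 subjects leave the peak and any-time rows (1.9 of 32.6 in mITT; 2.6 of 33.2 counting those dosed but not yet at Day 8). A small residual remains, because a titre could still rise between Day 29 and the Day 91 sample; a Day 91 cut-off would remove that too, but at the loss of about 8 subjects.

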#### **6.7. Multicenter Studies**

Not applicable. This study will take place at a single VTEU site (Emory University).

#### **6.8. Multiple Comparisons/Multiplicity**

No multiple comparisons correction will be applied for the interim analysis. No adjustments for multiple testing are planned for the final analysis.

## 7. STUDY SUBJECTS

### 7.1. Disposition of Subjects

The disposition of subjects in the study will be tabulated by vaccination group ([Table 14](#)). The table shows the total number of subjects screened, enrolled/randomized, vaccinated, received all vaccinations, completed Study Day 91, completed Study Day 181, completed final blood draw, completed follow-up (Study Day 381), and completed per protocol.

The composition of analysis populations, including reasons for subject exclusion, by vaccination group, will be presented in [Table 15](#). A listing of subjects excluded from each analysis population will be presented in [Listing 5](#).

Dates of first treatment administration by vaccination group will be presented in [Table 16](#).

[Table 17](#) will present a summary of the reasons that subjects were screened but not enrolled.

A Consort Diagram showing the disposition of study subjects will be included ([Figure 1](#)). This figure will present the number of subjects screened, randomized, excluded, discontinued treatment, terminated early, and analyzed, by vaccination group.

A listing of subjects who discontinued dosing or terminated from study follow-up, with reasons, will be included in [Listing 2](#).

### 7.2. Protocol Deviations

A summary of subject-specific protocol deviations will be presented by the reason for the deviation, the deviation category, and vaccination group for all subjects ([Table 6](#)). Deviations will be reviewed for possible subject exclusion from the per protocol population include: subject ineligibility at baseline (see Section 4.3.2 for subject exclusion criteria), a baseline rabies VNA concentration  $\geq 0.5$  IU/mL, study withdrawal or treatment discontinuation, an out-of-window treatment administration or study visit, receipt of non-study licensed live vaccine within 30 days before and following each study vaccination, receipt of non-study licensed inactivated vaccine within 14 days before and following each study vaccination, receipt of immunosuppressive therapy within 30 days before or following each study vaccination, and receipt of chloroquine or hydroxychloroquine. All subject-specific protocol deviations and non-subject specific protocol deviations will be included in [Appendix 3](#) as data listings ([Listing 3](#) and [Listing 4](#), respectively).

## 8. IMMUNOGENICITY EVALUATION

### 8.1. Primary Immunogenicity Analysis

Not applicable.

### 8.2. Secondary Immunogenicity Analyses

Summaries and analyses of immunogenicity data will be presented for the mITT population. If more than 5% of subjects, overall, would be excluded or have visits excluded from the PP population due to protocol deviations, then a PP analysis will also be performed.

Seroconversion is defined as achieving a serum antibody level post-vaccination that is greater than 0.5 IU/mL, the pre-defined protective titer in the KSU RFFIT assay.

Seroconversion rates and GMT for rabies VNA titers will be calculated for each antibody timepoint by vaccination group and will be summarized graphically.

Seroconversion rates and GMT will be presented with their corresponding 95% confidence interval estimates at each time point and overall peak GMT, and the pair-wise differences between seroconversion rates by treatment arm will be summarized by study day along with 95% CIs.

GMTs will be estimated by computing the geometric mean and 95% confidence interval based on the student's t distribution.

The distribution of antibody titers will also be graphically summarized using the reverse cumulative frequency distribution of titers by study day and vaccination group.

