5.2. Subject Exclusion Criteria

Subjects meeting any of the following exclusion criteria at baseline will be excluded from study participation.

1. Was ever vaccinated with a licensed or investigational rabies vaccine* or was diagnosed with rabies exposure, infection, or disease.

**Includes RABAVERT and Imovax. Subject's verbal history will suffice.*

2. Has a higher risk than the average US resident with regard to exposure to rabies, per the Rabavert package insert and rabies vaccination recommendations from the CDC*

**People at high risk of exposure to rabies, such as veterinarians, animal handlers, rabies laboratory workers, spelunkers, and rabies biologics production workers.*

**People whose activities bring them into frequent contact with rabies virus or with possibly rabid animals.*

**International travelers who are likely to come in contact with animals in parts of the world where rabies is common.*

3. Was ever vaccinated with a licensed or investigational Ad vector or Ad vaccine.
4. Is currently taking chloroquine or hydroxychloroquine²⁶
5. Was diagnosed with laboratory-confirmed COVID-19 (PCR or antigen-based test) in the preceding 28 days.
6. Positive serology for HIV antibody, HCV antibody, or Hepatitis B surface antigen (HBsAg).
7. Has known allergy or history of anaphylaxis or other serious adverse reaction to a vaccine or vaccine products*.

**Including egg products, aminoglycosides, gelatin, sorbitol, tris (hydroxymethyl)-amino methane (THAM), or any of the constituents of the study vaccines.*

8. Has severe allergy or anaphylaxis to latex.
9. Has an acute illness or temperature $\geq 38.0^{\circ}\text{C}$ on Day 1*.

**Subjects with fever or acute illness on the day of vaccination may be re-assessed and enrolled if healthy or only minor residual symptoms remain within 3 days.*

10. Female subjects who are pregnant or breastfeeding, or planning to become pregnant while enrolled in this trial and at least 60 days after last vaccination.
11. Has history of autoimmune disease, or clinically significant cardiac, pulmonary, hepatic, rheumatologic, or renal disease by history, physical examination, and/or lab studies.
12. Has history of malignancy other than squamous cell or basal cell skin cancer, unless there has been surgical excision that is considered to have achieved cure*.

**Subjects with a history of skin cancer must not be vaccinated at the previous tumor site.*

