### 3.2.2. Secondary

- Proportion of subjects seroconverting to rabies virus at each antibody time point (seroconversion is defined as VNA concentration  $\geq 0.5$  IU/mL), in each vaccination group and overall.
- GMT (as measured by rabies VNA using a standard, WHO-approved, RFFIT) at each antibody time point within each vaccination group.
- Peak GMT (as measured by rabies VNA using a standard, WHO-approved, RFFIT; peak GMT is defined as highest GMT measured across all post-vaccination antibody time points) within each vaccination group.

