## 3.3. Study Definitions and Derived Variables

Seroconversion is defined as a VNA concentration  $\geq 0.5$  IU/mL. Peak GMT is defined as the highest GMT measured across all post-vaccination antibody time points per subject.

The baseline value will be defined as the last value obtained prior to the first vaccination.

Vaccination group is defined as the four vaccine and dose combinations:

- Low Dose ChAd155-RG
- High Dose ChAd155-RG (x1)
- High Dose ChAd155-RG (x2)
- RABAVERT

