## 14.2 Immunogenicity Data

**Table 21: Rabies VNA Geometric Mean Titer and Seroconversion Rate with 95% Confidence Intervals by Time Point and Vaccination Group - Modified Intent to Treat Population\***

Time Point (day relative the vaccination)	Statistic	Low Dose ChAd155- RG (N=X)	High Dose ChAd155- RG (x1) (N=X)	High Dose ChAd155- RG (x2) (N=X)	Combined High Dose ChAd155-RG (N=X)	RABAVERT (N=X)
Day 1 (Baseline, Pre-Dose 1) a	n	x	x	x	x	x
	GMT	x.x	x.x	x.x	x.x	x.x
	95% CI for GMT	x.x, x.x	x.x, x.x	x.x, x.x	x.x, x.x	x.x, x.x
Day 8 (Pre-Dose 2) a	n					
	GMT					
	95% CI for GMT					
	Seroconversion (%) b					
	95% CI for Seroconversion					
Day 15 (Pre-Dose 3) a	n					
	GMT					
	95% CI for GMT					
	Seroconversion (%) b					
	95% CI for Seroconversion					
Day 22 (Pre-Dose 4) a	n				NA	
	GMT				NA	
	95% CI for GMT				NA	
	Seroconversion (%) b				NA	
	95% CI for Seroconversion				NA	
Repeat Day 22 for the following visits						
Day 29 (7 Days Post-Dose 4)					NA	
Day 91 (69 Days Post-Dose 4)					NA	
Day 181 (159 Days Post-Dose 4) c					NA	
Day 381 (359 Days Post-Dose 4) c					NA	
Peak Response, Post-Vaccination					NA	

Note: N = Number of subjects in the mITT population; n = number of subjects in the study population with data available at timepoint.

Exact (Clopper-Pearson) 95% CIs are presented for proportions.

aDay of study vaccination. Sample collected prior to vaccination.

bSeroconversion is defined as VNA  $\geq 0.5$  IU/mL post-vaccination.

cDay 181 time point will not be presented in the first interim immunogenicity analysis and Day 381 time point will not be presented in either interim immunogenicity analysis

Table with similar format:

**Table 22: Rabies VNA Geometric Mean Titer and Seroconversion Rate with 95% Confidence Intervals by Time Point and Vaccination Group - Per Protocol Population**

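### Seroconversion has no baseline condition, so a subject already at or above 0.5 IU/mL on Day 1 can count as a seroconverter in the mITT and interim analyses

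*SAP*

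**What the plan says.** The secondary endpoint in SAP 3.2.2 is "Proportion of subjects seroconverting to rabies virus at each antibody time point". SAP 8.2 gives the analysis definition: "Seroconversion is defined as achieving a serum antibody level post-vaccination that is greater than 0.5 IU/mL". Protocol 11.4.4 uses the same strict inequality, and so does the note to SAP Figure 8. SAP 3.3 ("Seroconversion is defined as a VNA concentration" of at least 0.5 IU/mL) and the Table 21 footnote ("Seroconversion is defined as VNA" of at least 0.5 after vaccination) include the boundary value, as do protocol 3.2.2 and SAP 3.2.2 and 4.5. All of these are thresholds on the level alone.

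On populations, SAP 8.2 states: "Summaries and analyses of immunogenicity data will be presented for the mITT population". SAP 6.3.1 defines mITT as "all subjects who received at least one dose of study vaccine and contributed both pre- and at least one post-study vaccination venous blood samples" with valid results. It requires a baseline sample but puts no bound on the value. The per-protocol (PP) rule in SAP 6.3.2 excludes "Data from subjects who have a baseline rabies VNA concentration" of 0.5 IU/mL or more. Under SAP 8.2 a PP analysis is added only if more than 5% of subjects overall lose some or all visits through deviations, and SAP 7.2 lists baseline VNA among those deviations. SAP 8.2.1 assigns PP Tables 22 and 24 and their figures without that condition.

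The interim immunogenicity review (SAP 6.6.2) uses mITT only. Tables 21 and 23 and Figure 8 are marked for the interim.

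At entry, prior rabies vaccination is an exclusion for which the subject's "verbal history will suffice" (protocol 5.2). The first RFFIT sample is taken on Day 1 before vaccination (protocol 7.3.1), and its result is not an eligibility criterion.

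**The concern.** The endpoint is named as a change but measured as a status. A subject who enters at or above the cut-off and stays there is scored as converted at each such visit without having responded to anything. The PP exclusion shows that the authors saw the problem, but the protection is missing from the main analysis and from the interim, which SAP 6.6 intends for conference presentation and early publication. Any error runs upward in the arm concerned. Through Table 23 it also enters the pairwise differences, in whichever direction the affected arm dictates. With 10 to 14 subjects per arm, a single misclassified subject is visible in the rate.

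**Working it through.** **Inputs.** Arms A=14, B=14, C=10, D=12, total 50 (SAP 5). Clopper-Pearson limits for rates and Miettinen-Nurminen limits for differences (SAP 8.2.1). PP trigger above 5% (SAP 8.2). The number of baseline-positive subjects, k, is not in the documents, so k = 1 or 2 per arm is an assumption for illustration.

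**The plan's own figures.** Clopper-Pearson limits with x = n × rate reproduce all 12 intervals of SAP Table 5 (protocol Table 4) to the whole percent. Examples: n=14 at 100% gives 76.84 to 100 (stated 77 to 100); n=10 at 90% gives 55.5 to 99.75 (stated 55 to 100).

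**Effect on one arm.** Let c be the converters among the n − k baseline-negative subjects, and assume the baseline-positives stay above the cut-off. As written, the rate is (c+k)/n. Among baseline-negatives it is c/(n−k). The difference is (k/n) × (1 − r), where r = c/(n−k). It is largest, at k/n, when nobody else has responded, and zero when everybody has.

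With k = 1 and no other responder:

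| Arm | As written (95% CI) | Baseline-negatives (95% CI) |
|---|---|---|
| A or B | 1/14 = 7.1% (0.2, 33.9) | 0/13 = 0% (0, 24.7) |
| C | 1/10 = 10.0% (0.3, 44.5) | 0/9 = 0% (0, 33.6) |
| D | 1/12 = 8.3% (0.2, 38.5) | 0/11 = 0% (0, 28.5) |

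Near a 50% rate with k = 1:
- A or B: 7/14 − 6/13 = 50.0 − 46.2 = 3.8 points.
- D: 7/12 − 6/11 = 58.3 − 54.5 = 3.8 points.
- C: 5/10 − 4/9 = 50.0 − 44.4 = 5.6 points.

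With k = 2 near 50%, the excess is 7.1 (A, B), 8.3 (D) or 10.0 (C) points. Near 90% with k = 1, it is 13/14 − 12/13 = about 0.5 points, or 9/10 − 8/9 = 1.1 points.

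**Effect on a difference (example).** A minus D as written, 8/14 against 12/12: −42.9 points (−67.8, −13.4). With the baseline-positive subject in A removed, 7/13 against 12/12: −46.2 (−71.3, −16.2).

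**PP trigger.** 5% of 50 is 2.5, so at least 3 affected subjects are needed (3/50 = 6%; 2/50 = 4%). One or two baseline-positives would not reach it on their own.

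**How likely is it?** For an assumed share q of baseline-positives, P(at least one of 50) = 1 − (1−q)^50:

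| Assumed q | At least one | Exactly one or two |
|---|---|---|
| 0.5% | 22% | 22% |
| 1% | 40% | 38% |
| 2% | 64% | 56% |
| 5% | 92% | 46% |

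**The cut-off.** A titer of exactly 0.5 IU/mL is seroconversion in Table 21 and not in Figure 8, although both report the same endpoint. This needs no assumption.

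**The case against.** The strongest reply is that the effect may never occur and would be small if it did. Entry bars prior rabies vaccine or diagnosed exposure, high-risk occupations and travel, and recent immunoglobulin, so baseline-positives may be absent. The endpoint is descriptive, with no formal hypothesis (protocol 11.1 and 11.2.2), and the exact interval at an observed 100% is already 23 points wide at n=14 (77 to 100). This stands, and it limits the weight of the point.

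The data would also not be hidden. Final Table 15 counts baseline VNA of 0.5 or more by group, Table 21 gives the Day 1 GMT, and Listing 9 shows every titer, so a careful reader could remove such a subject. That is true of the final report. At the interim, Table 15 covers only the safety and mITT sets, and listings are blinded to group.

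Three stronger readings are tempting, and the documents do not support them.

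- A reader might infer that 7 to 10 points are added at every visit. That is the ceiling; the excess shrinks as others respond and stops once the subject's own titer falls below the cut-off. Day 1 has no seroconversion row.
- A reader might infer that the PP analysis would not be run. The trigger counts every PP reason, including an out-of-window visit. With one baseline-positive subject, two more affected among 49 suffice. The chance is 1 − (1−p)^49 − 49p(1−p)^48, which is 71%, 96% or above 99% for an assumed deviation rate p of 5%, 10% or 20%. SAP 8.2.1 also lists the PP tables unconditionally. Even so, PP drops data for unrelated reasons and does not isolate this effect.
- A reader might infer that Days 8 and 15 are worst because true rates are low then. The only ChAd155-RG response data given in the protocol are in primates, where all 10 animals passed the threshold two weeks after one dose (protocol 2.1). Those are not human data, but they do not suggest a low Day 15 rate. Nothing is given for Day 8.

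**Conclusion.** The point holds as a flaw of definition. No wording of seroconversion has a baseline term, mITT does not supply one, and the only safeguard sits in a population that the interim does not use and that two SAP sections treat differently. The consequence is conditional and bounded: per baseline-positive subject, at most 7.1, 8.3 or 10 points by arm size, 3.8 to 5.6 near a 50% rate, 0.5 to 1.1 near 90%, and zero if all others convert. These figures assume that the subject's titer stays at or above the cut-off. The documents do not show that any such subject exists, so it cannot be said that the reported rates are in fact too high. The change should still be made, because the bias is avoidable and the baseline sample is already required. The conflict between greater than 0.5 and at least 0.5 is separate and certain.

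**What to change.** Choose one of two forms:

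1. Define seroconversion as baseline VNA below 0.5 IU/mL and post-vaccination VNA of at least 0.5 IU/mL, with baseline-negative mITT subjects as the denominator.
2. Keep the present measure on all mITT subjects, rename it *proportion with VNA ≥ 0.5 IU/mL*, and add the baseline-negative mITT rate.

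Under either form, flag baseline-positive subjects in the interim as well as the final report, and use at least 0.5 throughout. Make the change in SAP 3.2.2, 3.3, 4.5, 8.2, Table 21 and Figure 8. Align protocol 3.2.2 and 11.4.4, or record the departure in SAP section 15; changing the SAP alone would leave the two documents in conflict. Reconcile SAP 8.2 with 8.2.1 on whether the PP tables always appear. Settle all of this before group-unblinded data are analysed.

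The cost is wording in both documents and no new data. Under the first form the denominator may fall by one or two subjects; the second keeps mITT intact at the price of an extra row per visit.
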